# (2.2) Inclusion and exclusion criteria.

**a. Inclusion criteria.** Describe the specific criteria that will be used to decide who will be included in the research from among interested or potential subjects. Define any technical terms in lay language.

#### Phase 1

Phase 1 data analysis activities: Consumers seeking services from MHA and TS, English and/or Spanish speaking

Phase 1 Focus Group participants will be randomly chosen from MHA and TS English speaking consumers aged 18 and over

Phase 1 Talkspace Survey: English speaking TS consumers, aged 18 and over

#### Phase 2

Phase 2 micro-randomized trials (MRTs): Consumers seeking services from MHA and TS, English and/or Spanish speaking

Phase 2 focus groups: MHA and TS consumers aged 18 and over

• Talkspace only: Focus groups launching in November 2022 will focus on users' thoughts and reactions to receiving nudges (e.g., push notifications, emails) and their impact on engagement with the platform. For these focus groups only, inclusion criteria will be TS consumers aged 18 and over who have used Talkspace messaging-based therapy in the past 3 months, and have the Talkspace mobile app installed on their mobile device

## Phase 3

Phase 3b Study 1 SMART trial participants will be consumers seeking to take a mental health test from MHA and able to read English

Phase 3b Study 2 longitudinal survey participants will be consumers who have completed an English PHQ or GAD test from MHA and scored greater than or equal to 10 either of the measures. They will be 18 years or older, residing in the United States and who indicate that they have little or no familiarity with the concept of cognitive reframing.

**b. Exclusion criteria.** Describe the specific criteria that will be used to decide who will be excluded from the research from subjects who meet the inclusion criteria listed above. Define any technical terms in lay language.

#### Phase 1

Phase 1 data analysis activities: Non-English or Spanish speaking

Phase 1 Focus Group participants: non-English speaking, younger than 18

Phase 1 Talkspace Survey: Non-English speaking, younger than 18

## Phase 2

Phase 2 MRTs: non-English or Spanish speaking consumers

Phase 2 Focus Groups: non-English speaking, younger than 18

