## **Recruitment Procedures**

Potential participants will be shown an invitation to participate in this portion of the study and displayed on the screening results page for users after the PHQ-9 and GAD-7 mental health tests. If consumers are interested in learning more, they can respond to the invitation by clicking on a link, which will direct them to a landing page (displayed via REDCap survey) with more information about the study and the screening survey.

Screens/Surveys: All measures in this section will be completed using REDCap – refer to DOC: DIY Study – Measures for all measures listed in this section, and refer to DOC: Demographic questions for the demographics measure. Participants will receive links to complete these surveys via email and/or text message using Twilio, a REDCap extension that allows for SMS communication with participants. Participants will complete an initial screening assessment to determine eligibility, and then complete the same list of measures for 4 weeks while using intervention (consistent to each condition), an exit survey at week 5 and follow up measures consistent with the weekly measures at week 8 follow up. All participants will be asked to complete the demographics measure in addition to the measures included in the first week's battery of assessments.

Participants will be asked to complete the following measures in the screener:

- PHQ-9

- GAD-7
- Hopefulness Item
- Emotion Mechanisms

At the end of weeks 1-4 and week 8 follow up, participants will be asked to complete the following measures, some measures adjusted depending on condition:

- Questions Post DIY AI [DIY Tool, AI condition ONLY]
- PHQ-9
- GAD-7
- Hopefulness Item
- Emotion Mechanisms
- Competencies of Cognitive Therapy Scale Self Report
- Tool Use (sustain) [DIY Tool, No AI condition ONLY WEEKS 1-4, BOTH DIY TOOL CONDITIONS at WEEK 8]
- Tool Use (AI) [DIY Tool, AI condition ONLY, JUST WEEKS 1-4]

Demographics Measure (just week 1)

At week 8 only, participants will be asked the following questions (in addition to those previously approved):

- What is your total annual household income? (Less than \$20,000; \$20,000 \$39,999; \$40,000 \$59,999; \$60,000 \$79,999; \$80,000 \$99,999; \$100,000 \$149,999; \$150,000 or more; Prefer not to answer)

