#### **Randomization Procedures**

Once consenting to the study, upon beginning the REDCap screening survey, potential participants will automatically be randomly assigned to one of three conditions. This random assignment will not impact their screening process, eligibility, or the consent process. Their randomly assigned condition will not be revealed to them until after they consent to the study. Upon their consent, the information will be delivered to them via email, informing them of their assigned condition, outlining the study tasks and payment structure.

The three conditions are as follows: Control condition with psychoeducational reading material, a DIY worksheet, or a DIY tool with artificial intelligence, and are all concerned with the idea of thinking traps and learning how to apply the concept of cognitive reframing to situations in one's own life. Folks in both DIY tool conditions will be prompted to use their tools 3x a week, and all participants will be asked to respond to weekly surveys for the duration of 4 weeks.

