5.7) Protected Health Information (PHI). Will participants' identifiable PHI be accessed, obtained, used, or disclosed for any reason (for example, to identify or screen potential subjects, to obtain study data or specimens, for study follow-up) that does not involve the creation or obtaining of a Limited Data Set?

PHI is individually identifiable healthcare record information or clinical specimens from an organization considered a "covered entity" by federal HIPAA regulations, in any form or media, whether electronic, paper, or oral. You must answer yes to this question if the research involves identifiable health care records (e.g., medical, dental, pharmacy, nursing, billing, etc.), identifiable healthcare information from a clinical department repository, or observations or recordings of clinical interactions.

Χ

No

→ If no, skip the rest of this question; go to question 5.8

Yes

→ If yes, answer all of the questions below.

a. Describe the PHI and the reason for using it. Be specific. For example, will any "free text" fields (such as physician notes) be accessed, obtained, or used?

MHA is not a covered entity, therefore no information included in the MHA dataset is not considered PHI. Talkspace is a covered entity, thus information included in the TS dataset is considered PHI. This information includes demographics such as age, gender, marital status, race/ethnicity, income status and education; PHQ9 (depression); GAD7 (anxiety); Prodromal Questionnaire-Brief Version (PQ-B; psychosis); Brief Bipolar Test; SWED (eating disorders); PC-PTSD (PTSD); CAGE-AID (Substance Use Disorder); Work Health Survey; caregiver status; the Duke Social Support Scale, a measure of perceived social support; and meta-data collected from consumers' interaction with the TS website. Only members of TS' study team will have access to any identifiable information, with the exception of information provided during the Phase 1 Talkspace Survey.

Phase 3B Study 2 ONLY: PHO-9 scores, GAD-7 scores are used in the screening process for the study in REDCap and to determine eligibility for the study.

APPLICATION IRB Protocol

b. I	Is any of the PHI located in Washington State?			
	X No			
	Yes			
	Describe the pathway of how the PHI will be accessed or obtained, starting with the ource/location and then describing the system/path/mechanism by which it will be identified,			
	accessed, and copied for the research. Be specific. For example: directly view records; search			

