- MHA Focus Groups: After viewing/receiving the invitation, consumers indicate their interest by clicking on the invitation and completing a brief survey. A member of the study team emails interested participants the consent form and to provide information about the focus group, which is all done online including instruction, options for anonymity, and any recording that may happen. Verbal consent is collected at the beginning of each remote focus group.

Phase 1 Talkspace Survey: After clicking on link in the invitation, potential respondents will review a brief statement that describes the survey, procedures, voluntariness, opportunity to ask questions, and compensation potential. This text has been uploaded to Zipline ("Talkspace\_Nudge Survey\_MHATS"). Respondents then indicate consent by clicking a box that specifically states they consent to the survey.

Phase 3B Study 2: After clicking on the study invitation, completing the initial screening questionnaire on REDCap and learning eligible status, informed consent will be obtained electronically via REDCap. Participants will review the consent and provide consent online. Participants are encouraged to contact the study team via email if parts of the informed consent form are unclear, or if additional information is desired. Consent will be documented in REDCap. Participants must select that they agree to participate in the study at the end of the consent form in order to move forward with study procedures.

**c.** Comprehension. Describe the methods that will be used to ensure or test the subjects' understanding of the information during the consent process.

Phase 1 & Phase 2 FOCUS GROUPS ONLY: Potential participants will be given ample opportunity to ask questions of MHA and TS study staff.

Phase 1 Talkspace Survey: Contact information for the study team at both TS and UW is provided.

Phase 3B Study 2: Contact information for the study team at UW is provided, and participants are encouraged to contact the team with any questions.

**d.** Influence. Does the research involve any subject groups that might find it difficult to say "no" to participation because of the setting or their relationship with someone on the study team, even if they aren't pressured to participate?

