ENHANCING ENGAGEMENT WITH DIGITAL MENTAL HEALTH CARE

STUDY00010958

07/03/2024

NCT04507360

Aim 3B Statistical Analysis Plan. For Study 1, all research questions were examined via logistic regressions. We assessed whether participants' first condition (i.e., demographics survey or Next Steps survey) predicted the odds of disengagement. Within participants who completed the demographics survey, we examined whether the odds of disengaging and clicking a featured resource on the screening results page significantly differed for participants in the Tailored Resources to Demographics condition compared to control (i.e., Generic Response + Generic Resources). Within participants from the Next Steps survey condition, we tested whether engagement significantly differed for participants shown Tailored Response + Generic Resources, Generic Response + Tailored Resources to Desired Resources, and Tailored Response + Tailored Resources to Desired Resources compared to control. We aimed to identify the optimal tailoring strategy by comparing engagement across all tailoring conditions, with Tailored Resources to Demographics set as the reference group. For Study 2, research questions were examined via t-tests and Cohen's d effect sizes comparing engagement, short-term restructuring effectiveness, longer-term effectiveness (e.g., skill acquisition, reductions in depression and anxiety), and heterogeneous treatment effects by condition (i.e., control, DIY tool without AI, and DIY tool with AI).

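### Study 2 names only t-tests for depression and anxiety; adjusting for the screener score should be more precise, by an amount the documents do not fix

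*SAP*

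**What the plan says.** The SAP gives Study 2 one sentence: "For Study 2, research questions were examined via t-tests" with Cohen's d, comparing engagement, short-term restructuring effectiveness, longer-term effectiveness and heterogeneous effects by condition. Longer-term effectiveness is described as "longer-term effectiveness (e.g., skill acquisition, reductions in depression and anxiety". No covariate, regression or longitudinal model is named for Study 2, no week is named, and reductions is not defined.

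The protocol's schedule is in 5.1 (Study 2, Screens/Surveys) and is repeated in 5.4:
- "Participants will be asked to complete the following measures in the screener": the list includes PHQ-9 and GAD-7.
- "At the end of weeks 1-4 and week 8 follow up, participants will be asked to complete the following measures": PHQ-9 and GAD-7 appear again, now with the cognitive-therapy competency scale, which is not in the screener.

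On timing, 8.2.b places consent after the screener: participants reach it after "completing the initial screening questionnaire on REDCap and learning eligible status, informed consent will be obtained electronically via REDCap". 5.1 (Randomization Procedures) has assignment generated as the screener begins, but "Their randomly assigned condition will not be revealed to them until after they consent to the study". 8.7 confirms that assignment comes before consent and disclosure after it.

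On entry, 2.2.a requires that the person "scored greater than or equal to 10 either of the measures", and 5.7.a says that PHQ-9 and "GAD-7 scores are used in the screening process for the study in REDCap and to determine eligibility for the study".

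**The concern.** A screener score taken before the arm is known is usually a good predictor of the same score weeks later. A t-test on follow-up scores ignores it. A t-test on change scores uses it, but with a fixed weight of 1. Regression adjustment estimates the weight and so should give a smaller standard error than either.

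The protocol (5.1, Study 2) says that it is not known whether the tool improves mental health functioning, and the PHQ-9 and GAD-7 comparisons address that question. With three groups and 300 people, or 250 in 2.1 and 4.1, precision in each pairwise comparison is limited. At stake are somewhat wider intervals and lower power than the data allow.

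**Working it through.** The documents give no power, alpha, SD, correlation or allocation ratio for Study 2, so there is no planned figure to reproduce. Everything below is conditional.

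**Inputs**
- From the protocol: 300 people, three groups; entry at 10 or more on either scale.
- Assumed: equal allocation (100 per arm), two-sided 5%, 80% power, complete data, the same screener/follow-up relation in each arm, normal scores with equal SDs before selection, entry cut at the mean of each scale, PHQ/GAD correlation 0.7, untruncated screener/follow-up correlation ρ of 0.4, 0.6 or 0.8.

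**Step 1: t-test on follow-up scores.** The two-sample t-test at 100 per arm detects d = 0.398, in units of the follow-up SD among those enrolled.

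**Step 2: effect of the entry rule on the screener SD.** Let B be the screener score and G the other scale, both standard normal.
- Probability that both are below the cut: 1/4 + arcsin(0.7)/(2π) = 0.3734, so 0.6266 enter.
- Mean of B among entrants: 0.3989 × 0.5 × 1.7 / 0.6266 = 0.541.
- Mean of B² among entrants: [1 − (0.3734 + 0.7 × 0.714/6.283)] / 0.6266 = 0.873.
- Variance: V = 0.873 − 0.541² = 0.580, against 1 before selection.

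**Step 3: relative variances among entrants.** Follow-up variance is ρ²V + 1 − ρ². Write r for the observed correlation and k for screener SD over follow-up SD.
- Follow-up t-test: 1. Change-score t-test: 1 − 2rk + k². Adjusted: 1 − r².
- Change minus adjusted is (r − k)², which cannot be negative. The direction is therefore secure, apart from one degree of freedom.
- Detectable d is 0.398 times the square root of the relative variance.
- The gain in equivalent participants is the variance ratio minus 1. Here it reduces to ρ²V/(1 − ρ²) over follow-up scores and V(1 − ρ)/(1 + ρ) over change scores.

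| ρ before selection | r | k | d, follow-up | d, change | d, adjusted | gain over change | gain over follow-up |
|---|---|---|---|---|---|---|---|
| 0.4 | 0.32 | 0.79 | 0.398 | 0.422 | 0.378 | 24.9% | 11.1% |
| 0.6 | 0.50 | 0.83 | 0.398 | 0.370 | 0.346 | 14.5% | 32.6% |
| 0.8 | 0.71 | 0.89 | 0.398 | 0.288 | 0.279 | 6.4% | 103.1% |

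For example, at ρ = 0.6 the gain over change scores is 0.580 × 0.4/1.6 = 0.145. A simulation of the same model with 2,000,000 draws gave 25.1%, 14.4% and 6.4% over change scores, and 11.0%, 32.6% and 103.0% over follow-up scores.

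**Step 4: sensitivity.** The 45 scenarios use a cut at −0.5, 0 or +0.5 SD; entry on the measure itself, or on either scale with PHQ/GAD correlation 0.5 or 0.7; and ρ from 0.4 to 0.8.
- Gain over change scores: 3% to 33%. The maximum is at ρ = 0.4; at ρ = 0.8 it is at most about 9%.
- Gain over follow-up scores: 5% to 137%. The maximum is at ρ = 0.8.

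At 83 per arm (250 in total), the follow-up t-test detects d = 0.437, and the adjusted analysis 0.42, 0.38 and 0.31.

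**Step 5: where the gain vanishes.** Over follow-up scores it is 1/(1 − r²) − 1: 1% at r = 0.1 and 4% at r = 0.2. Over change scores it is zero when r = k, that is, when the slope of follow-up on screener is 1.

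**The case against.** The best defence is that nothing in the SAP sentence is wrong. A t-test in a randomised comparison is valid with complete data, and choosing ANCOVA can look like preference. Reductions most naturally means change from the screener, so the baseline is probably in use already; detectable d then moves by only 0.01 to 0.04 in the cases above. Every input that sets the size is assumed. The SAP is in the past tense, so the analysis may be finished. All of this stands. It limits the point to an optional improvement, but does not remove it: the direction is secure and the covariate is already collected.

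Three stronger readings are tempting, and the documents do not support them.
- A reader might infer that the t-tests are biased or invalid. Randomisation protects them, and nothing here shows bias from drop-out.
- A reader might infer that adjustment would double the effective sample. That needs t-tests on follow-up scores and an untruncated correlation near 0.8; the documents establish neither.
- A reader might infer that assignment at the start of the screener spoils the score as a baseline. The condition stays hidden until after consent, so the participant's answers cannot respond to it.

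One simplification: the protocol applies the cut to the website test (4.1) and again in REDCap (5.7.a), while the model truncates once. Trying a double cut moved the middle change-score gain only from 14.5% to 14.2%.

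**Conclusion.** The point holds as a modest loss of efficiency for PHQ-9 and GAD-7. Adjustment for the screener score is expected to be more precise than either form of t-test, with almost no gain over follow-up scores if the correlation is near zero and almost none over change scores if the slope is near 1. On the more natural change-score reading, the gain is 3% to 33% in equivalent participants across the assumed scenarios. The follow-up-score reading gives a wider range, whose upper end should not be quoted alone.

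The conclusion on direction needs only randomisation and a screener score unaffected by arm. The sizes rest on the normal truncation model and on assumed correlations, allocation and power. Engagement and the cognitive-therapy competency scale have no screener value and gain nothing. The change is worth making but not required; confidence in its size is moderate at best.

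**What to change.** - For PHQ-9 and GAD-7, at whichever weeks the t-tests are made (for example week 4 and week 8), replace the t-test with an ANCOVA: follow-up score on condition and the screener score of the same measure, in eligible, consented, randomised participants.
- Report adjusted pairwise differences with 95% confidence intervals beside Cohen's d, and the number per arm without a score at that week.
- State the weeks, and whether any unadjusted result shown is a follow-up or a change score.
- Do the same for the Hopefulness Item and Emotion Mechanisms only if they are analysed as outcomes. The SAP does not name them, and their scoring is not shown in these documents.
- If the t-tests have been run, keep them, add the adjusted analysis on the existing data, and label it post hoc.

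The cost is close to nil: one covariate already collected, in a standard regression. No new data are needed, and no pairwise contrasts are added beyond those the t-tests make.

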analyses on over 10,000 TS consumers to identify engagement patterns that determine initial predictors of DMH engagement. TS collected the PHQ-9 on consumers every 3 weeks. Completion of these measures is a good indicator of clinical engagement in treatment. Results indicated engagement was a function of plan type and symptom severity. Of the three plan types, weekly video chat had the largest early disengagement, with only 17% of those enrolled engaged longer that 6 weeks (fig 2a). 40% of consumers initiate treatment but do not engage for 3 weeks, 21% do not engage longer than 6 weeks and another 12% do not engage past 9 weeks. Only 2% engage for a full year (fig 2). Consumers who exhibit more symptoms at intake assessment are less likely to disengage from treatment, with the odds of disengagement decreasing by 3.3% for each additional point on intake PHQ-9. However, higher symptoms over the course of care results in greater disengagement, with the odds of disengagement increasing by 5.3% for each additional point on the final PHQ-9 assessment completed. Both MHA and TS are highly motivated to understand engagement and the impact engagement has on clinical outcomes.

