Phase 3b Study 2 MHA longitudinal survey participants: Participants will be compensated up to \$40-60 in the form of Amazon gift cards for their participation in the study, with the total potential amount depending on their randomly assigned mental health resource condition. For participants in the control condition, they will earn up to \$40 total across the 6 surveys they complete after consenting – they will earn \$5 for each of the surveys in weeks 1-4, and \$10 for the exit survey in Week 5 and \$10 for the follow up survey at week 8. For both DIY tool conditions, they will be eligible to earn up to \$60 for their participation, and they will be compensated for the surveys the same as those in the control. DIY condition participants will also be eligible for an additional \$5 each week for the first four weeks of the study, which will be awarded when they use the DIY tool at least 3 times in the week. Payments for all participants will be split up into 6 sections and sent out on a weekly basis. Payment will not be dependent on completion of the entire study, and \$5 payments will solely be based on completion of surveys (and engagement with DIY tool for relevant conditions) at each timepoint. This distribution method requires only the participants' email address. UW will be responsible for the distribution of these incentives.

(4.5)Non-monetary compensation. Describe any non-monetary compensation that will be provided. Example: extra credit for students; a toy for a child. If class credit will be offered to students, there must be an alternate way for the students to earn the extra credit without participating in the research.

N	/	A

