## **Randomization sequence**

The drafted randomization sequence is outlined on the MHA SMART Flow.pdf uploaded to zipline. Participants will be randomized first between a standard demographics survey to start or demographics along with a mini quiz focusing on asking a participant's primary website action intention (e.g., reading more about depression, connecting with therapists, using a DIY tool) and perceived need to do something to improve their mental health. Participants will then be randomized to types of screening results pages, with combinations of tailored responses and resources based on their responses to the demographics quiz and/or the mini quiz. For instance, if the participant chooses to continue to visit further content, they will be randomized to conditions of different presentations of a DIY question or tool on the page. Length of engagement, bounce rates, and other variables listed under metadata collection will be used to examine the impact of tailoring on engagement, which conditions and combinations of conditions result in increased engagement, and how the use of DIY tools impact engagement.

## Study 2

As previously proposed in Aim 3, we have developed an AI tool that uses machine learning / NLP / AI methods to personalize and tailor an intervention to improve engagement and completion outcomes. We focus on a specific, popular DIY tool (~10,000 users /month) that teaches cognitive restructuring. Our pilot work found that (1) engagement and completion rates on DIY tools can be low, and (2) a pilot AI tool had significantly higher engagement and completion rates. These differences may arise due to AI support, UI/UX/design differences, other factors, or a combination thereof. Additionally, the efficacy of the digital tool to improve mental health functioning is unknown. Study 2 will recruit 300 participants who will be randomly assigned to one of three groups for a longitudinal month-long study: twice-weekly DIY tool use with AI, without AI, or a control group.

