10.8 Withdrawal of participants. If applicable, describe the anticipated circumstances under which participants will be withdrawn from the research without their consent. Also, describe any procedures for orderly withdrawal of a participant, regardless of the reason, including whether it will involve partial withdrawal from procedures and any intervention but continued data collection or long-term follow-up.

n/a

(10.9) Anticipated direct benefits to participants. If there are any direct research-related benefits that some or all individual participants are likely to experience from taking part in the research, describe them below:

Do not include benefits to society or others, and do not include subject payment (if any). Examples: medical benefits such as laboratory tests (if subjects receive the results); psychological resources made available to participants; training or education that is provided.

n/a

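### Study 2 plans only t-tests for symptom and skill outcomes, with no analysis set, time point or missing-data method; a repeated-measures model on scores already collected would be more precise and less exposed to drop-out

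*SAP*

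**What the plan says.** The SAP's Study 2 plan is a single sentence: "research questions were examined via t-tests and Cohen's d effect sizes comparing engagement, short-term restructuring effectiveness, longer-term effectiveness". Longer-term effectiveness is illustrated as "e.g., skill acquisition, reductions in depression and anxiety", and the sentence ends with "heterogeneous treatment effects by condition (i.e., control, DIY tool without AI, and DIY tool with AI". No model, baseline adjustment, analysis population, primary time point or missing-data rule is given, there or in the protocol.

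The protocol sets out the design and the data:

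- **Size.** Section 5.1: "Study 2 will recruit 300 participants who will be randomly assigned to one of three groups for a longitudinal month-long study". Sections 2.1 and 4.1 give 250 instead; the two figures must be reconciled.
- **Measures.** PHQ-9 and GAD-7 are in the screener. Section 5.1 then says: "At the end of weeks 1-4 and week 8 follow up, participants will be asked to complete the following measures", a list that includes both scales and the cognitive therapy skill scale. The skill scale is not in the screener.
- **Burden.** Both DIY arms are prompted to use a tool several times a week (section 5.1 gives two different frequencies, which must be reconciled). Control is asked to read material at the start.
- **Drop-out.** Section 1.8b reports on Talkspace clients, "with the odds of disengagement increasing by 5.3% for each additional point on the final PHQ-9 assessment completed", and odds 3.3% lower per intake point. No drop-out figure is given for Study 2.

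**The concern.** A two-sample t-test at a survey wave can use only those who answered that wave. PHQ-9 is scheduled 1 + 4 + 1 = 6 times. Someone who leaves after week 3 has four scores on file, yet contributes nothing to a week 8 contrast, on raw or on change scores.

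Two costs follow. The first is certain: information that has been collected is not used, so standard errors are larger than they need be. The second is conditional. If people with worse symptoms leave more often, and the rate or mechanism of leaving differs by arm, those who remain are no longer comparable, and the arm that loses more of its unimproved participants looks better.

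The documents make that plausible. Section 1.8b links leaving to PHQ-9 and treats PHQ-9 completion as a marker of engagement. Section 5.1 reports higher engagement and completion with the pilot AI tool. Task burden differs by arm once the arm is revealed. At stake are the DIY-versus-control symptom and skill contrasts, and AI versus no AI if the tools retain people differently.

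**Working it through.** The plan gives no power calculation, SD or drop-out figure to reproduce, so the size is shown over a range.

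**Inputs from the protocol.** Odds ratios for leaving: 1.053 per point on the last PHQ-9 and 0.967 per intake point (section 1.8b, Talkspace). Scores at the screener, weeks 1-4 and week 8 (section 5.1).

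**Assumptions.** 100 per arm (300 divided equally; no ratio is stated). Loss by week 8 of p0 = 20% in control and p1 = 40% in a DIY arm. Week 8 PHQ-9 SD 5 to 6, intake SD 4, correlation 0.5. Two-sided 5% test.

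**1. Bias at the protocol's odds ratios, no true effect.** If the log-odds of leaving rise by b per point of the week 8 score, the mean of those who remain falls by about p × b × SD². With the same b in both arms:

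bias ≈ −(p1 − p0) × b × SD², with b = ln 1.053 = 0.0516

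- SD 5: 0.2 × 0.0516 × 25 = 0.26 (numerical integration: 0.25)
- SD 6: 0.2 × 0.0516 × 36 = 0.37 (0.36)

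Adding the intake ratio, ln 0.967 = −0.0336, with covariance 0.5 × 4 × SD:

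- SD 5: 0.2 × (0.0516 × 25 − 0.0336 × 10) = 0.19 (0.19)
- SD 6: 0.2 × (0.0516 × 36 − 0.0336 × 12) = 0.29 (0.29)

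So the raw week 8 contrast is off by 0.19 to 0.36 points in favour of the arm that loses more people. Change scores are off by 0.15 to 0.27. With equal loss and the same mechanism in both arms, the bias is zero.

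**2. Simulation.** Drop-out after each weekly survey depends on scores already observed; week 8 SD is 5.6.

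| Scenario | Raw week 8 t-test | Change-score t-test | Likelihood model |
|---|---|---|---|
| Protocol ratios in both arms, true effect −1.5 | −1.60 to −1.65 | −1.53 | −1.47 to −1.50 |
| No true effect; loss linked to symptoms in DIY only, odds ratio 1.10 to 1.15 | false benefit 0.7 to 1.25; rejects 11% to 26% | false benefit 0.1 to 0.4; rejects 5% to 8% | within 0.07 of zero |

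**3. Check on the rejection rates.** With 80 and 60 completers, SE = SD × √(1/80 + 1/60) = 0.171 × SD. The rejection rate is Φ(−1.96 + δ) + Φ(−1.96 − δ), with δ = bias/SE.

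- Bias 0.36, SD 6: δ = 0.36/1.02 = 0.35, about 6.4%
- Bias 0.7, SD 5.6: δ = 0.7/0.96 = 0.73, about 11%
- Bias 1.25, SD 5.6: δ = 1.25/0.96 = 1.31, about 26%

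**4. Precision.** In these simulations, a repeated-measures model with the screener score as covariate had a standard error 5% to 11% below the change-score t-test and 7% to 24% below the raw one. Another set of runs gave 3% to 12% below the raw one. Since 1/0.95² = 1.11 and 1/0.89² = 1.26, the gain over change scores is worth 11% to 26% more participants.

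**5. Pay.** Surveys pay 4 × 5 + 10 + 10 = 40 dollars in every arm. The DIY arms can add 4 × 5 = 20 dollars, making 60, but that part depends on tool use: "which will be awarded when they use the DIY tool at least 3 times in the week".

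**The case against.** The strongest reply is that the SAP speaks of reductions in depression and anxiety, which points to change from the screener. On that reading the false benefit is 0.1 to 0.4 points and the test stays near its nominal level. This stands, and it limits the bias argument. It does not answer the loss of precision, and the SAP does not actually state which score is tested.

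Three further points also stand. The Talkspace ratios come from therapy clients on a platform that takes no part in Aim 3B, and the two ratios run in opposite directions. The 20% and 40% losses, and selection confined to the DIY arm, are assumptions. The simulation makes drop-out depend on observed scores, which suits a likelihood model by construction; in step 1 drop-out depends on the week 8 score itself, and there such a model would not remove all the bias.

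A reader might infer two stronger things that the documents do not support.

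- **That the arms are paid differently for answering surveys.** Section 4.4 pays the same for surveys in all arms. Only the tool-use bonus differs, and its effect on survey response could go either way.
- **That nobody who stops the tool is followed.** Section 10.8 is answered n/a, but its words on "including whether it will involve partial withdrawal from procedures and any intervention but continued data collection or long-term follow-up" are the form's printed prompt. Section 4.4 pays survey by survey regardless of completing the study, section 5.1 asks all participants for weekly surveys, and section 5.11 sends reminders throughout. Nothing ends surveys when tool use stops.

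**Conclusion.** The point holds as a choice of method that should be changed. The Study 2 plan names only t-tests and Cohen's d. It leaves the analysis set, time point and missing data undefined, and by default discards repeated scores that the study collects. The loss of precision follows from the design: roughly 5% to 11% in standard error against a change-score test under the correlations assumed.

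Bias is a risk, not an established fault. With assumed losses of 20% and 40%, it is about 0.1 to 0.35 PHQ-9 points at the Talkspace odds ratios. Under stronger selection confined to the DIY arm it is about 0.1 to 0.4 with change scores, and about 0.7 to 1.3 only with raw week 8 scores. It would be wrong to conclude that the DIY contrasts are known to be biased, since no document states how many people leave Study 2 or why. Only PHQ-9 was worked through; for GAD-7 and the skill scale the argument carries over in kind, without a size.

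**What to change.** For PHQ-9, GAD-7 and the skill scale, replace the t-tests with one mixed model for repeated measures per outcome:

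- **Terms:** arm, week and arm-by-week, with unstructured covariance, and the screener score as covariate where collected. The skill scale has none.
- **Analysis set:** all eligible, consented participants in their assigned arm with at least one follow-up score. This needs stating because section 8.7 places random assignment before consent.
- **Estimates:** arm differences at week 4 and week 8 with confidence intervals. Cohen's d can be kept by dividing each difference by a named SD.
- **Reporting:** survey completion by arm and week, including those with no follow-up score.
- **Sensitivity:** one missing-not-at-random analysis, for example worsening the missing DIY scores by a stated range of points.

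No new participants, measures or procedures are needed. The SAP is written in the past tense, so this can be a reanalysis of existing data, labelled as such. The cost is analyst time and revised SAP text. The downside is that the model assumes data are missing at random given the observed scores, which is why the sensitivity analysis is needed.
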